**CONFIDENTIAL**

204837

- EP Hgb values will be computed and compared across treatment groups using the primary ANCOVA model described above. Rubin's rules [Rubin, 1987] will be used to combine results of the imputed datasets using SAS PROC MIANALYZE procedure. As a result, a single estimated treatment difference and its standard error will be produced, with which a 95% CI will be calculated.

**Model Checking & Diagnostics**

- Distributional assumptions underlying the model used for analysis will be examined by obtaining a normal probability plot of the residuals and a plot of the residuals versus the fitted values (i.e. checking the normality assumption and constant variance assumption of the model respectively) to gain confidence that the model assumptions are reasonable.
- If there are any departures from the distributional assumptions, alternative models will be explored using appropriate transformed data, if justified.
- Models will be examined for treatment interactions with baseline Hgb and stratification factor.
- For multiple imputation model checking and diagnostics, refer to Model Checking & Diagnostics for Tipping Point Analysis

**Model Results Presentation**

- All available observed Hgb values (on and off-treatment) will be summarized using mean, standard deviation, minimum, P25, median, P75 and maximum at each visit by treatment group. In addition to scheduled visits, the baseline value and mean EP, mean Alt. EP, and end of treatment will be included (see Section 14.6.3).
  - This summary of Hgb by visit will be repeated for central laboratory Hgb values only and for HemoCue Hgb values only.
  - This display will also be repeated for visits up to and including Week 52, using the data used for the primary Hgb analysis (i.e., including imputed values).
- All available observed Hgb change from baseline values (on and off-treatment) will also be summarized using mean, standard deviation, minimum, P25, median, P75, and maximum at each post-baseline visit, including the mean EP, mean Alt EP and end of treatment values (see Section 14.6.3).
  - This display will be repeated for visits up to and including Week 52, using the data used for the primary Hgb analysis (i.e., including imputed values).
- The number and percentage of subjects with imputed data in the primary Hgb analysis will be provided by treatment group. The number and percentage of subjects by reason for data imputation will be provided. Reasons include: intermittent missing Hgb values, death before Week 28, death during Week 28 – 52, investigator site closed before Week 28, investigator site closed during Weeks 28-52, lost to follow-up before Week 28, lost to follow-up during Week 28 – 52, consent withdrawn before Week 28, consent withdrawn during Week 28 – 52, and other monotone missing Hgb values. Subjects will be further classified as either having observed all 7 scheduled EP Hgb values, having observed a partial schedule of EP Hgb values, having observed no scheduled EP Hgb values with at least one unscheduled EP Hgb value, or having observed no EP Hgb values, scheduled or unscheduled. For subjects with partial scheduled EP Hgb values, both the pattern of imputed data (intermittent, monotone) and the amount of imputed data (1 – 6 scheduled Hgb values missing) will be summarized. For subjects with partial scheduled EP Hgb values and a monotone imputed data pattern, the reason for the monotone imputed scheduled EP Hgb

**CONFIDENTIAL**

204837

values will be provided. Reasons include: death during Week 28-52, investigator site closed during Weeks 28-52, lost to follow-up during Week 28 – 52, consent withdrawn during Week 28 – 52, and other monotone imputed Hgb values. And for summaries of the amount of missing scheduled EP Hgb values, the presence or absence of additional unscheduled EP Hgb values will be summarized.
 
 
• The least square (LS) mean estimates and standard errors by treatment group, LS mean difference, two-sided 95% CI and one-sided non-inferiority p-value for the difference in the primary Hgb endpoint between the daprodustat and rhEPO arms from the ANCOVA model will be presented. The number of subjects contributing to the analysis and the associated mean and standard deviation of the baseline and EP Hgb values will also be displayed with the results of the ANCOVA model.
 
• The LS mean difference and associated two-sided 95% CI will be displayed on a forest plot together with supportive analysis results (excluding the Tipping Point Analysis).
 
• All available mean Hgb values (on and off-treatment, observed and imputed) will be displayed graphically for each scheduled study visit using a line plot. The line plot of mean values and 95% CI by time will include horizontal reference lines to depict the hemoglobin analysis range (10-11.5 g/dL), vertical reference lines to identify the EP (weeks 28-52), and the number of subjects by treatment group contributing to each mean value.
 
• All available Hgb change from baseline values (on and off-treatment, observed and imputed) will be displayed graphically for each scheduled study visit using a line plot. The line plot of mean values and 95% CIs by time will include vertical reference lines to identify the EP (Weeks 28-52), and the number of subjects by treatment group contributing to each mean value.
 
• A listing of all hemoglobin values will be provided, including treatment, most recent dose, site ID, unique subject ID, subject ID, visit, assessment date, selected demographic information and central laboratory and HemoCue Hgb values.
 

Model Results Interpretation
 
Non-inferiority will be achieved if the lower limit of the two-sided 95% CI of the treatment difference is greater than the pre-specified non-inferiority margin of -0.75 g/dL.


Sensitivity Statistical Analyses
 
Tipping Point (Multiple Imputation) Analysis
 
 
• Tipping point analysis will be performed using all available Hgb values (on and off-treatment) as a sensitivity analysis for the primary estimand.
 
• Tipping point analyses will be conducted under a range of missing data assumptions to determine how extreme assumptions need to be for non-inferiority conclusions to change. Assumptions about missing Hgb values on the daprodustat and rhEPO arms will vary independently, and will include scenarios where subjects with missing data on daprodustat have worse outcomes than subjects with missing data on rhEPO. 
 
○ Intermittent missing scheduled Hgb data in both arms through Week 52 will be imputed using PROC MI procedure with NIMPUTE = 200 and MCMC IMPUTE = monotone to generate 200 datasets with only monotone missing patterns. Burn in iterations (NBITER) and maximum iteration (MAXITER) will both be set to 500. The seed for reproducibility is set to 204837. The imputations will be done by study treatment, and region.
 
 
 

---

CONFIDENTIAL

204837

- For each of the monotone missing dataset (out of the 200 imputed as indicated above), the missing scheduled Hgb values in both arms through Week 52 will be imputed based on the MAR assumption and will be performed using PROC MI by treatment, and region. The monotone regression will include baseline Hgb, prior scheduled (possibly imputed) Hgb values, and may have region as a covariate (see Model Checking & Diagnostics, below). The seed for reproducibility is set to 204837.
- For each treatment arm separately, the imputed monotone missing Hgb values will vary from the MAR scenario by a multiple of delta, where delta represents a change in Hgb over a 4-week interval. No delta adjustments will be done for intermittent missing values. Beginning with the first missed visit (which could occur before Week 28), for every 4-weeks, the imputed Hgb value would shift an additional delta (for every 2-week interval, the imputed Hgb value would shift an additional 0.5 delta instead). For example, if the first missed visit is after Week 8, the first missed visit will use delta, the second missed visit will use 2\*delta, etc. If the first missed visit is on or before Week 8, the first missed visit will use 0.5 delta, the second missed visit will use either (0.5+0.5)\*delta, or (0.5+1)\*delta depending on the 2- or 4-week interval in between the two visits, etc. The deltas explored for each treatment arm will range from -4 g/dL to 4 g/dL per 4-week interval with a 0.5 g/dL increment respectively. Delta scenarios which are known ahead of time not to possibly represent the tipping point may not be explored.
- The low and high cutoffs at Hgb values of 6 g/dL and 15 g/dL will be applied to all imputed Hgb values.
- EP Hgb values will be computed for each pair of deltas and compared across treatment groups using the primary ANCOVA model described above (including unscheduled visit). Rubin's rules [Rubin, 1987] will be used to combine results of the imputed datasets using SAS PROC MIANALYZE procedure. As a result, for each pair of delta values, a single estimated treatment difference and its standard error will be produced, with which a 95% CI can be calculated.

#### **Model Checking & Diagnostics (for Multiple Imputation and Tipping Point Analyses)**

- Intermittent missing data imputation:
  - If there are error and or warning messages related to the by statement (e.g. not enough observations to fit regression models), try by study treatment only.
  - If convergence issue occurs, the convergence precision may be set to 1E-3.
- Monotone missing data imputation:
  - When imputing for each of the monotone missing dataset (out of 200), if there are error and or warning messages related to the by statement and/or regression model (e.g. not enough observations with the Monotone statement), try 1) by study treatment with baseline Hgb and region as covariates, 2) impute by study treatment with baseline Hgb as covariates, until no error/warning messages.

#### **Model Results Presentation (for Tipping Point Analysis)**

- The delta pairs, their corresponding model-adjusted mean Hgb change from baseline to EP in the two treatment arms, the model-adjusted treatment difference, and two-sided 95% CI will be presented. The non-inferiority conclusion will be drawn if the lower confidence limit of the two-sided 95% CI is greater than -0.75, which will also be presented in the tables.

CONFIDENTIAL

204837

- Graphics depicting treatment difference and non-inferiority surfaces will be produced using an enhanced tipping point approach [Liublinska, 2014]; A colored heat map that illustrates the gradual change of treatment difference will be produced. Green borders will be used to highlight the delta combinations that result in rejecting the null hypothesis (i.e., non-inferiority established).

Supportive Statistical Analyses
While On-Treatment Evaluable Hgb Analysis

 
• Alternative “while on-treatment” estimand using only evaluable Hgb data (see Section 14.6.3): 
 
○ This estimand utilizes the same endpoint, summary measure and target population as the primary Hgb estimand. For the intercurrent events of deaths, study treatment discontinuation, use of non-randomized ESA medication for any reason including rescue, and blood transfusions, a “while-on-treatment” strategy will be used.
 
○ This estimand reflects the effect of daprodustat treatment relative to rhEPO, while on treatment and without the use of non-randomized ESA medication or blood transfusions
 
○ For this analysis, the primary Hgb analyses and summaries described above will be performed using evaluable Hgb values (see Section 14.6.3). .
 
○ No data will be imputed in this analysis, so a summary of missing data will be provided instead of a summary of imputed data.
 
○ The LS mean treatment difference and associated two-sided 95% CI from this analysis will be included on a forest plot with the primary Hgb analysis results.
 
○ The number and percentage of subjects meeting each evaluable Hgb (see Section 14.6.3) exclusion criteria will be summarized by scheduled visit.
 
○ A tipping point analysis similar to the one described above will be performed as a sensitivity analysis for this estimand using evaluable Hgb values only.
 
 
 

PP Population Analysis

 
• The while on treatment evaluable Hgb analysis and summaries described above (with the exception of the missing data summary) will also be performed using the PP population and evaluable Hgb values (see Section 14.6.3).
 
• The LS mean treatment difference and associated two-sided 95% CI from this analysis will be included on a forest plot with the primary Hgb analysis results
 

Alternative EP (Week 28-36) Analysis

 
• The following analyses will be repeated using an alternative EP from Week 28-36: 
 
○ The primary analysis and summaries (using on- and off-treatment, observed and imputed, Hgb values (see Section 14.6.3)
 
○ Supportive analyses and summaries of the alternative estimand that uses evaluable Hgb values and a while-on-treatment strategy for handling intercurrent events will be repeated using an alternative EP from Week 28-36.
 
 
 
• Summaries of imputed/missing Hgb values will not be repeated.
 
• The LS mean treatment difference and associated two-sided 95% CI from these analyses will be included on a forest plot with the primary Hgb analysis results.
 

**Subgroup Analysis**

- Subgroup analysis will be performed using all available observed and imputed Hgb values (on and off-treatment), and Rubin's rules [Rubin, 1987] will be used to combine results of the imputed datasets using SAS PROC MIANALYZE procedure.
- Subgroup analysis will also be performed separately using evaluable Hgb values only (see Section 14.6.3).
- Subgroup analysis details are discussed in Section 5.4.2.

**7.2. Principal Secondary Efficacy Analyses****7.2.1. Endpoint / Variables**

Average monthly IV iron dose (mg)/participant to Week 52

**7.2.2. Summary Measure**

Model-adjusted mean treatment difference (LS mean difference) in average monthly IV iron dose (mg)/participant to Week 52.

**7.2.3. Population of Interest**

The principal secondary efficacy analyses will be based on the All Randomized (ITT) population, unless otherwise specified.

**7.2.4. Strategy for Intercurrent (Post-Randomization) Events**

The treatment effect to be estimated will be effect while the participants were on their initial study treatment. All IV iron use from Day 1 to Week 52 up to the time of study treatment discontinuation will be included in the principal secondary efficacy analyses.

**7.2.5. Statistical Analyses / Methods**

Details of the planned displays are provided in [Appendix 10: List of Data Displays](#) and will be based on GSK data standards and statistical principles.

Unless otherwise specified, endpoints / variables defined in Section 7.2.1 will be summarised using descriptive statistics, graphically presented (where appropriate) and listed.

CONFIDENTIAL

204837

**7.2.5.1. Statistical Methodology Specification**

Endpoint / Variables

 
• Average monthly IV iron dose (mg)/participant to Week 52
 

Model Specification

 
• Average monthly IV iron dose (mg)/participant to Week 52 will be determined by calculating the total IV iron dose per subject from Day 1 to Week 52 while the participant was on study treatment and dividing by (the number of days the participant was on study treatment/30.4375 days). See Section 14.4.1 for the definition of on-treatment IV iron.
 
• An ANCOVA model will be used to compare the difference in average monthly IV iron dose per participant between arms, adjusting for: 
 
○ Treatment
 
○ Baseline monthly IV iron dose (see Section 5.2.1)
 
○ Region (as randomized, see Section 5.3 & Section 5.4.1)
 
 
 

Model Results Presentation

 
• The number and percentage of subjects with baseline IV iron use, on-treatment EP IV iron use, and on-treatment IV iron use to Week 52 will be summarized by treatment. Boxplots by study treatment will be created separately for on-treatment average monthly IV iron dose to week 52 and for post-randomization average monthly IV iron dose to week 52.
 
• Average monthly IV iron dose at baseline, while on treatment during the EP, and while on treatment to Week 52 will be summarized by treatment group using mean, standard deviation, minimum, P25, median, P75, and maximum.
 
• The least square (LS) mean estimates and standard errors by treatment group, LS mean difference, two-sided 95% CI and one-sided superiority p-value for the difference in average monthly IV iron dose/subject to Week 52 between the daprodustat and rhEPO arms from the ANCOVA model will be presented. The number of subjects contributing to the analysis and the associated mean and standard deviation of the baseline and Week 52 values will also be displayed with the results of the ANCOVA model.
 
• A listing of average monthly IV iron dose will be provided including treatment, site ID, unique subject ID, subject ID, time period, and average monthly IV iron dose at Week 52.
 

Model Results Interpretation

 
• Conditional on the primary endpoint achieving non-inferiority at the one-sided 2.5% level, statistical testing will progress to the principal secondary endpoint with a focus on superiority using a one-sided 2.5% significance level.
 

Supportive Statistical Analyses
Average monthly IV iron dose (mg)/subject to Week 52 using on and off treatment IV iron records

 
• The summaries and analysis described above for the principal secondary average monthly IV iron dose/subject to Week 52 will be repeated using all available IV iron records during the Day 1 – Week 52 visits, regardless of whether or not a subject was on treatment (i.e. treatment policy estimand).
 
• The average monthly IV iron dose (mg)/subject to Week 52 for this analysis will be determined by calculating the total IV iron dose per subject from Day 1 to Week 52 and
 

Supportive Statistical Analyses
dividing by (earliest of the (Week 52 visit date, study completion/withdrawal date) – Randomization date + 1 day/30.4375 days).
Subgroup Analysis

 
Subgroup analyses will be performed for the principal secondary endpoint using ANCOVA model with terms for treatment group, baseline IV iron dose, region, subgroup and treatment by subgroup interaction. Subgroup analysis details are discussed in Section 5.4.2.
 
Subgroup analysis results will be presented graphically using a forest plot.
 

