2. SCHEDULE OF ACTIVITIES (SOA)

Table 1 Schedule of Activities

Procedure Visit window of ± 3 days for Weeks 2 to 8, and ± 1 week for all other visits. All visit timings are relative to Day 1. All assessments will be performed pre-dialysis unless otherwise specified.	Screening (Week -4)	Treatment Period: Day 1 through Week 52					Follow-up Visit (4 to 6 weeks after last dose)
		Day 1 ¹	Full Study Visit Week 4, 16, 28, 40	Abbreviated Study Visit Week 2, 6, 8, 12, 20, 24, 32, 36, 44, 48	Week 52	Unscheduled ²	
Informed consent	X						
IRT system transaction ³	X	X	X	X	X	X	X
Inclusion and exclusion criteria	X	X					
Randomization ⁴		X					
Study Treatment Dispensing ^{5,6}		X	X	X ⁷		X ⁷	
Study Treatment Compliance ⁶			X	X ⁷	X	X ⁷	
Participant reminder to report changes in health ⁸		X					
Medical history (including past and current medical conditions, hospitalization and transfusion) ⁹	X						
Demography, height	X						
Weight (pre- and post-dialysis) and EDW ¹⁰	X	X	X	X	X	X	X
SBP/DBP, HR (pre- and post-dialysis)	X	X (triplicate)	X	X	X (triplicate)	X	X
Kt/Vurea ¹¹		X	X		X		
12-lead ECG ¹²	X				X		
Ultrasound of kidneys and adrenal glands ¹³	X						
Estradiol and FSH (females only, if required) ¹⁴	X						
Serum pregnancy test (WOCBP only) ^{15,16}	X	X	X		X		X
HemoCue Hgb	X	X	X	X	X	X	
Hematology ¹⁷	X	X	X	X (Hgb only)	X	X	X
Clinical chemistry ¹⁷	X	X	X		X	X	X
Ferritin, total iron and UIBC ¹⁷	X	X	X		X		X

Procedure Visit window of ± 3 days for Weeks 2 to 8, and ± 1 week for all other visits. All visit timings are relative to Day 1. All assessments will be performed pre-dialysis unless otherwise specified.	Screening (Week -4)	Treatment Period: Day 1 through Week 52					Follow-up Visit (4 to 6 weeks after last dose)
		Day 1 ¹	Full Study Visit Week 4, 16, 28, 40	Abbreviated Study Visit Week 2, 6, 8, 12, 20, 24, 32, 36, 44, 48	Week 52	Unscheduled ²	
Lipids (non-fasting) ¹⁷		X	X		X		
iPTH, hsCRP, HbA1c ^{17, 18}		X	Wk 28		X		
Hepcidin ^{17, 19}		X	Wk 4, 16, 28		X		
PD: EPO, VEGF ¹⁷		X	X (once from Wk 28 to Wk 52) ²⁰				
PK		X	X (once from Wk 8 to Wk 52) ²¹				
Stored samples for biomarkers ²²		X	Wk 28		X		
Genetic sample ²³		X					
Patient Global Impression of Severity (PGI-S) ²⁴		X	Wk 28	Wk 8, 12	X		
Patient Global Impression of Change (PGI-C) ²⁴			Wk 28	Wk 8, 12	X		
Non-serious AEs, SAEs, AEs of Special Interest, clinical events	X ²⁵	X	X	X	X	X	X
Concomitant medication review	X	X	X	X	X	X	X
Iron therapy, transfusions, rescue medications ^{26, 27}	X	X	X	X	X	X	X

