7.8.1. Iron Management Criteria

Participants must remain iron replete throughout the study. The investigator will follow the iron management criteria from randomization (Day 1) through Week 52 for participants who are receiving study treatment.

From Day 1 onwards, iron therapy will be administered if ferritin is ≤ 100 ng/mL and/or TSAT is $\leq 20\%$. The investigator should choose the route of administration and dose of iron based on the participant's iron status and local clinical practice.

All iron (excluding multivitamins) must be stopped and cannot be administered if:

- Ferritin > 800 ng/mL and TSAT $> 20\%$, or
- TSAT $> 40\%$

Investigators should be guided by local/regional guidelines and may stop administration of iron at a lower ferritin or TSAT level as long as participants are maintained at a ferritin > 100 ng/mL and TSAT $> 20\%$.

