Category	Subgroups																														
Age	<65 years, ≥65 to <75 years, ≥75 years																														
Gender	Female, Male																														
Race group	American Indian or Alaskan Native, Asian, Black, Native Hawaiian or Other Pacific Islander, White, Mixed Race																														
Ethnicity	Hispanic, non-Hispanic																														
Region	Regions listed in Appendix 7																														
Country	Countries listed in Appendix 7																														
Dialysis vintage	0 to <2 years, 2 to <5 years, ≥5 years																														
Prior rhEPO dose	<7,000 U/week, ≥7,000 U/week																														
rhEPO Hypo-responsiveness	No, Yes (see RAP for definition)																														
Baseline Hgb	<9 g/dL, 9 to <10 g/dL, 10 to 11 g/dL, >11 g/dL																														
BMI	<30 kg/m ² , ≥30 kg/m ²																														
Weight	< 75kg, ≥75kg																														
Baseline hsCRP	≤3 mg/L, >3 mg/L																														
United States	US, Non-US																														
Principal Secondary	Conditional on the primary endpoint achieving non-inferiority at the one-sided 2.5% level, statistical testing will progress to the principal secondary endpoint with a focus on superiority using a one-sided 2.5% significance level.																														

Endpoint	Statistical Analysis Methods
	For the principal secondary endpoint of average monthly IV iron dose up to Week 52 endpoint, IV iron use for all participants will be recorded in the eCRF and the average monthly IV iron dose up to week 52 while on treatment will be calculated. An ANCOVA model will be used to compare the difference in this average monthly IV iron dose per participant between arms, including factors for baseline dose, treatment and the randomization stratification factor.
Secondary	All analyses of secondary endpoints are of exploratory nature. Summary statistics along with nominal one-sided p-values and two-sided 95% confidence intervals will be used to describe the results.
Exploratory	Will be described in the reporting and analysis plan
Patient Reported Outcomes	Analysis to compare the participant reported effects of daprodustat and rhEPO on symptoms, as discussed in Section 9.9, will be described in the RAP.

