### 5.4. Examination of Covariates, Other Strata and Subgroups

#### 5.4.1. Covariates and Other Strata

The list of covariates and other strata may be used in descriptive summaries and statistical analyses, some of which may also be used for subgroup analyses. Additional covariates and other strata of clinical interest may also be considered.

Category	Details
Strata	Regions listed in Section 5.3.
Covariates	Baseline Hgb (For the analysis of the primary endpoint and other analyses of Hgb-related endpoints)  For subgroup analyses, statistical models will be adjusted for the covariates used in the original analysis (randomization stratification factor and baseline hemoglobin), subgroup, treatment and treatment by subgroup interaction (see Section 5.4.2 for the subgroup variables.).

Randomization is stratified by the prognostic factor, region, which will be taken into account within the analysis models.

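### The principal secondary IV iron ANCOVA is valid but leaves out baseline ferritin and TSAT, which could be prespecified at almost no cost and may improve precision

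*SAP*

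**What the plan says.** The endpoint in SAP 7.2.1 is "Average monthly IV iron dose (mg)/participant to Week 52", counted while on study treatment. SAP 7.2.5.1 sets the model: "An ANCOVA model will be used to compare the difference in average monthly IV iron dose per participant between arms, adjusting for". Three terms follow: region, treatment and the baseline value of the outcome, given as "Baseline monthly IV iron dose (see Section 5.2.1"). Protocol 10.3.1 agrees, "including factors for baseline dose, treatment and the randomization stratification factor". Ferritin and TSAT appear in neither model and are not among the subgroups in SAP 5.4.2.

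Protocol 7.8.1 governs iron during the study. "From Day 1 onwards, iron therapy will be administered if ferritin is" 100 ng/mL or below and/or TSAT is 20% or below. At the other end, "All iron (excluding multivitamins) must be stopped and cannot be administered if" ferritin is above 800 ng/mL with TSAT above 20%, or TSAT is above 40%. Between these limits the investigator chooses dose and route, guided by iron status and local practice.

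The Schedule of Activities (Protocol Section 2, Table 1) has "Ferritin, total iron and UIBC" at screening and on Day 1, and the central laboratory calculates TSAT (SAP 14.6.3.2). SAP 5.2.1 already defines a Day 1 baseline for iron parameters. SAP 5.4.1 adds a general permission: "Additional covariates and other strata of clinical interest may also be considered".

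**The concern.** The outcome is an amount of iron given, and the protocol ties the giving of iron to two laboratory values. Both values are known before the first dose, yet neither is in the model. Baseline IV iron dose records past prescribing, and region may pick up some local practice, but no term measures iron status at the start.

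Prior dose is also not a full substitute. It covers the 12 weeks before randomization (SAP 5.2.1 and 14.6.3.2), whereas the protocol's iron rules apply from Day 1. The exclusion criteria in Protocol 6.2 set a lower limit on ferritin and TSAT but no upper limit. A participant who received much iron recently can therefore be randomized already above a stop limit. Prior dose alone would point to high on-study use in that person; iron status would point to low use.

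At stake is precision. This is the one superiority test under multiplicity control (SAP 5.5), and the sample size was set on hemoglobin and on exposure (Protocol 10.1.1). No SD, effect size or power is given for IV iron.

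**Working it through.** **1. The plan's own figures.** These concern hemoglobin only. With SD 1.5 g/dL and 360 evaluable participants split 240:120, the half width is 1.96 × 1.5 × √(1/240 + 1/120) = 0.329 g/dL (stated: 0.33). The most negative passing difference is −0.75 + 0.329 = −0.421 g/dL (stated: −0.42). At SD 1.5, power for true differences of 0, −0.1, −0.2 and −0.3 is 99.4, 97.2, 90.7 and 76.5% (stated: >99, 97, 91 and 76%). There is no corresponding figure for IV iron to reproduce.

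**2. Inputs for IV iron.** Allocation is 268:134, N = 402 (Protocol 10.1.1), and the test is one-sided at 2.5% (SAP 5.5). Participants who are never treated have no value (SAP 14.6.3.2), so 402 is an upper bound. The planned model has 7 parameters (intercept, treatment, baseline dose and four for the five regions), leaving 402 − 7 = 395 residual degrees of freedom. Two continuous covariates reduce this to 393.

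**3. Assumption.** Let R² be the share of residual variance that baseline ferritin and TSAT explain beyond baseline IV iron dose and region. The documents do not give it, so a range from 0 to 0.20 is shown.

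**4. Formulas.** The standard error ratio is √(1 − R²), and the equivalent sample size is 402/(1 − R²). In residual SD units, the standard error under the planned model is √(1/134 + 1/268) = 0.1058. The planned model has 80% power at an effect of 0.2971 residual SD and 90% power at 0.3438. Power with the covariates comes from the noncentral t distribution with 393 degrees of freedom at those same effects.

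| Assumed R² | SE ratio | SE reduction | Power, from 80% | Power, from 90% | Equivalent N |
|---|---|---|---|---|---|
| 0 | 1.000 | 0% | 80.0% | 90.0% | 402 |
| 0.01 | 0.995 | 0.5% | 80.4% | 90.3% | 406 |
| 0.02 | 0.990 | 1.0% | 80.8% | 90.6% | 410 |
| 0.05 | 0.975 | 2.5% | 82.0% | 91.4% | 423 |
| 0.10 | 0.949 | 5.1% | 84.0% | 92.7% | 447 |
| 0.20 | 0.894 | 10.6% | 88.0% | 95.2% | 502 |

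Starting from 80% or 90% power with 240:120 instead of 268:134, the resulting powers are the same to the precision shown.

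**5. Cost.** A rough break-even for two extra terms is 2/395 = 0.005. Below that R² the covariates buy nothing, but they also lose almost nothing.

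**The case against.** The strongest reply is that nothing is wrong with the plan. The model adjusts for the baseline value of the outcome and for the stratification factor, as the protocol specifies. In a randomized comparison, leaving out a further prognostic variable does not bias the estimate or inflate type I error, and chance imbalance is already reflected in the standard error. All of this stands. A reader might infer from the omission that the test is invalid; the documents do not support that.

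A reader might also infer that ferritin and TSAT must be strong predictors, so that precision is materially lost, or that they fix iron use whatever the prior dose. The documents show neither:

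- Between the limits, dose is left to the investigator, who may also stop iron at lower levels. Prior dose and region are reasonable proxies for that practice.
- Low ferritin or TSAT at screening excludes the participant (Protocol 6.2), which thins out the low end.
- The limits act on repeated values during the study, and the outcome averages up to 52 weeks. One baseline value is only one input.
- Low iron status may be treated orally, which does not count toward the endpoint.
- The limits are joint step rules, which two linear terms need not capture.

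These points may well keep R² small. They do not remove the high-end mechanism, since there is no upper entry limit.

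Nor is this the only superiority test in the plan. Other secondary endpoints are tested for superiority at a nominal level (SAP 2.2); it is the only one under multiplicity control.

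Finally, SAP 5.4.1 leaves room for more covariates. That is a permission that names no variable, and it does not prespecify the model for a gatekept test.

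**Conclusion.** The point holds as an efficiency improvement, not as the correction of an error. The planned three-term model is valid, and no shortfall in power has been shown. Baseline ferritin and TSAT are the measurements on which the protocol starts and stops iron, they are already collected, and prior dose does not fully stand in for them.

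The size of the gain is unknown. At an R² of 0.05 or less it is at most 2 percentage points of power from an 80% starting point; at 0.20, the top of the assumed range, it is 8 points. The result rests on the assumed R², on a planned model that happens to have 80% or 90% power, and on an approximately linear relation. Because the cost is so low, a modest and uncertain gain is enough to justify the change.

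**What to change.** Before unblinding, add baseline log(ferritin) and baseline TSAT as continuous covariates in SAP 7.2.5.1 to three models: the principal secondary ANCOVA, its supportive repeat using on- and off-treatment iron records, and the subgroup ANCOVA, which lists its own terms and would otherwise no longer match.

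Use the general baseline rule in SAP 5.2.1, which takes the last available value before dosing up to the randomization date, so that a screening value carries forward if Day 1 is missing. Both measurements are needed at screening for eligibility, so few participants should lack a value.

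Record the change as a row in SAP Table 1, since the model would then differ from Protocol 10.3.1. That table already records a larger change, to the primary hemoglobin analysis. The cost is these edits and two degrees of freedom out of 395; no new data are needed.
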